## **XIV. WITHDRAWAL OF PARTICIPANTS**

Situations in which the entire study may be terminated early include the following: If the Principal Investigator or other governing official discovers serious concerns about subjects' safety, inadequate performance or rate of enrollment (this includes a missed study session); because study objectives have been obtained according to pre-established statistical guidelines; or in the unlikely event that the Principal Investigator retires and no other additional investigators are able to succeed his role within the research project.

Though highly unlikely, the circumstances under which a participant would be withdrawn without his or her consent include: obviously not following instructions or behavior that is verbally or physically abusive towards research staff. Those who experience early withdrawal will receive prorated payment based on the number of sessions they completed.

## **XV. RISKS TO PARTICIPANTS**

---

### **Risks Associated with Venipuncture.**

There is a small risk of local hematoma, infection, and syncope associated with phlebotomy.

### **Risks Pertaining to the Collection of Genetic Material.**

The collection of genetic material (i.e. from the blood) entails risks to confidentiality. Ethical guidelines for the collection and use of genetic material continue to develop; however, set guidelines for these purposes have yet to be officially set forth. The collection of genetic material has become common-place within several research disciplines, and entails only minimal risk to study participants.

### **Risks Pertaining to Liver Function Panel Tests.**

There is a risk that the liver function panel test will reveal a result concerning an individual research participant beyond the scope of the study protocol due to a critical value level obtained from the blood work. In the event of Boulder Community Hospital Reference Laboratory obtaining a critical value level result, personnel from BCH will contact [name] with the subject number and test results. [name] will then share this information with the participant, which will likely be distressing to them.

### **Risks Pertaining to fMRI Scans.**

The MRI scanning procedure in a 3 Tesla system has been approved by the FDA and is safe for use in healthy human populations and there are no known risks associated with the visual or auditory stimuli presented during recording of functional MRI. There are however, several risks both physical and psychological, involved in the use of fMRI. These shall be explained to the participants during screening and consent processes:

### **Physical Risks and Discomforts.**

- The magnetic field of the MR environment has the potential to cause burns or bodily injury if ferrous metal objects are implanted in the body, or if personal articles containing ferrous material are brought into the environment.
- Participants who could suffer potential risks include those with metal implants (pacemaker, metal rods, bone screws, orthodontics, metal flakes from metalworking).

- Participants who might be pregnant may be at risk during the MRI procedure. The risk of MRI to pregnant women and fetuses is currently unknown.
- Participants have the potential to experience discomfort due to scanner noise.
- Participants will be told that they may experience discomfort from lying in one position for a long time. The discomfort should subside once the scan is complete, but some subjects may be sore for a more extended duration.
- Participants will be informed about peripheral nerve stimulation (PNS/tingling) that they may experience during the scan. At sufficient exposure levels, peripheral nerve stimulation is perceptible as “tingling” or “tapping” sensations.

### **Psychological Risks and Discomforts.**

- There is some risk of feeling nervous or claustrophobic while participants are in the scanner.
- There is a risk that the image will reveal an observation concerning an individual research participant that has potential clinical importance but is beyond the aims of this protocol. In the event of the confirmation of a significant anomaly in a participant’s brain image, this information will likely be distressing to the participant.

### **Exposure to Alcohol.**

During the fMRI scan at baseline and the second follow-up visit, participants are exposed to less than a teaspoon of an alcoholic beverage, there is a risk that participants may experience an urge to drink or it might cause cravings or anxiety. This risk is particularly relevant during the second MRI scan because many patients may have established abstinence or reduced their alcohol consumption substantially.

### **Risks Pertaining to Loss of Confidentiality and Privacy.**

Confidentiality of participants is a priority for research staff and must be maintained unless the investigator obtains the express permission of the subject to do otherwise. Risks from breach of confidentiality include invasion of privacy, as well as social and economic risks. Economic risks include alterations in relationships with others that are to the disadvantage of the subject, and may involve embarrassment, loss of respect of others, labeling with negative consequences, or diminishing the subject's opportunities and status in relation to others. These risks include payment by subjects for procedures, loss of wages or income, and/or damage to employability or insurability.

Participants will be asked about illegal activities that they may have been involved in (i.e. illicit drug use). Participants will also be warned that there are some things that they might tell us that we CANNOT promise to keep confidential. Participants will be informed that we are required to report information like child abuse or neglect, crimes that they tell us they or others plan to commit, or harm planned against yourself or others.

Self-report data will be collected via individual laptop computers. Theft of the study computers is also a possibility, but an extremely unlikely risk.

Participants must be 21 years of age in order to participate in the study. For this reason, participants’ driver’s licenses will be checked at the beginning of the first study session to ensure that they are 21 years of age. In order to protect confidentiality, a copy of the license will not be retained.

### **Unanticipated risks.**

Any experiment may involve risks that cannot be anticipated. If unanticipated risks occur, the investigators will follow the IRB guidelines for adverse event reporting the risks, discomforts, hazards

or inconveniences to the participants.

## **XVI. MANAGEMENT OF RISKS**

---

Participants are informed of all procedures beforehand, and they must read the informed consent form and sign the consent form stating that they understand and agree to the procedures before beginning the study.

### **Protection against risks associated with Venipuncture.**

The risks of hematoma and infection are minimized by having trained phlebotomist perform all blood draws along with using standard and sterile phlebotomy techniques.

### **Risks Pertaining to the Collection of Genetic Material.**

The collection of genetic material has become commonplace within several research disciplines, and entails only minimal risk to study participants. All genetic material will be coded and stored with a randomly generated number. The master list linking the numbers to participants' names will be stored on a password-protected server. At study closure, all links between participant name and URSI will be destroyed, at which point the specimen/data will be considered de-identified. Participants will be informed, both verbally and in writing upon initial consent, of the risks of genetic research.

### **Risks Pertaining to Liver Function Panel Tests.**

In the unlikely event of a critical value level test result, BCH will inform [name] of the participant's randomly generated participant number and abnormal test result. [name] will immediately inform the participant of the test results and share a copy of the results for the participant to give to their primary care physician or a referred specialist. Participants will be informed of this risk associated with the liver function test during the consenting process and made aware that we will be unable to clinically interpret the results past informing them that they indicate critical value levels.

### **Risks Pertaining to fMRI Scans.**

This protocol will be performed using an MR scanner employing pulse sequences and hardware that have been approved by the FDA for human clinical use. The field strength is 3 Tesla and all relevant operating characteristics (RF power deposition, rate of change of the field gradients, coil design) fall within the limits of FDA guidelines for NMR exposure.

In the case of an anomalous finding in a brain image, the following procedure is followed:

1. The technologist and/or research personnel flag potential abnormalities.
2. The MRI technologist notifies the INC Director of Operations, appropriate Georgia State University (GSU) personnel, and the P.I.
3. The scan gets queued to the radiologist worklist in COINS. All cases of suspected incidental findings are sent for formal neuroradiologic review at GSU.
4. The radiology review contains a written summary of the findings and classifies the referral status into one of these categories:
  - o There is not enough information from the MRI scan to complete a full review. No obvious abnormalities found.
  - o MRI shows nothing obvious that needs medical attention.

- MRI shows something that may or may not be of medical concern. Participants should consider discussing the enclosed report with their doctor.
- MRI shows something that needs to be brought to the attention of your doctor. Participants may also be contacted by the study team and/or appropriate GSU personnel about this report.

5. The PI will get an electronic copy of the radiology review (coded via URSI) as soon as the review is completed. If an urgent referral is recommended, the PI should discuss the review with the Medical Director prior to contacting the participant.
6. If a referral is recommended, the PI will contact the participant and explain that an unusual feature was observed in their scan. The PI provides the contact information for the Medical Director who reviewed the image (this information is in the letter mailed to the participant as well). Routine referrals are handled on a case by case basis and up to the PI/Medical Director to determine if the participant should receive a call in advance.
7. All cases reviewed will generate a formal radiology report, which is printed on letterhead and a copy of which is mailed to the participant. In the case of an urgent referral, someone from the study team or the Medical Director will contact the participant prior to the letter being mailed

### **Physical Risks and Discomforts.**

- Participants who could suffer potential risks include those with metal implants (pacemaker, metal rods, bone screws, orthodontics, metal flakes from metalworking). Participants are carefully screened for these types of metal implants or any other bodily exposure to metal during informed consent, and again prior to the MR scan, using an MRI safety screening checklist. It will be clearly explained to participants that the magnetic field of the MR environment has the potential to cause burns or bodily injury if ferrous metal objects are implanted in the body, or if personal articles containing ferrous material are brought into the environment. MR Facility rules strictly forbid staff from entering the magnet room carrying metal objects.
- Female participants will be warned that the risk of MRI to pregnant women and fetuses is currently unknown. Study staff will explicitly inform all female participants of this fact and they will be given the option to complete a free urine pregnancy test. Female subjects who test positive will not be allowed to participate in the study. The pregnancy test will be strongly recommended by the study staff. If the participant wishes to dismiss the request to complete a urine pregnancy test, they must sign an agreement to acknowledge the risk and indicate that they do not believe they are currently pregnant. This will be required immediately prior to the MRI scan.
- Participants will be informed about potential discomfort they may experience due to scanner noise. This risk will be minimized by providing participants with earplugs and headphones. Ultimately, the volume of the noise is not great enough to pose a health risk, with or without earplugs/headphones.
- Participants will be told that they may experience discomfort from lying in one position for a long time. The discomfort should subside once the scan is complete, but some subjects may be sore for a more extended duration.

- Participants will be informed about peripheral nerve stimulation (PNS/tingling) that they may experience during the scan. At sufficient exposure levels, peripheral nerve stimulation is perceptible as “tingling” or “tapping” sensations. It will be made clear to participants that PNS symptoms usually subside shortly after the scan is completed. In addition, participants are given a squeeze ball to use in case of an emergency. They are informed that if they experience PNS related sensations or are otherwise uncomfortable, they can alert the MRI technologist via the squeeze ball and the technologist will stop the scan immediately.

### **Psychological Risks and Discomforts.**

- There is some risk of feeling nervous or claustrophobic while participants are in the scanner. This risk will be minimized by (1) including exclusion criterion for claustrophobia in the phone pre-screen, (2) informing participants before they enter the scanning room that they may stop the scan at any time, (3) providing participants ear protection with headphones, a mirror to see out, a button to signal distress, and an intercom and (4) making sure the subject is lying comfortably with head and neck supported. Scan time will be kept to a minimum.
- There are psychological risks associated with potential incidental findings that may show up in the scan images. For example, there is a risk that an image may reveal an observation concerning an individual research participant that has potential clinical importance but is beyond the aims of the study. In the event of the confirmation of a significant anomaly in a participant’s brain image, this information will likely be distressing to the subject and constitutes a psychological risk.

### **Exposure to Alcohol.**

During the fMRI session, participants may experience a reaction to the alcohol presented to them during the scan. Such a reaction might manifest as craving or anxiety. These effects are almost always only temporary. We have used the same cue exposure task in over 600 participants; many of who were treatment-seeking patients who had established some measure of abstinence (required to be in our studies) prior to scanning. We have not observed any adverse effects from our cue exposure protocol in these individuals. It is important to understand that the entire task uses less than 1 tsp of an alcohol beverage. The consent form clearly notes that the cue exposure session takes place at baseline and at the second follow-up session (week-32) and clearly notes that patients can opt out of the cue exposure part of the study. The patients will be reminded again about the option to opt out of the MR scan. As we have done previously, we will conduct an assessment with each participant after the cue exposure session to determine whether there is any residual craving or anxiety. We also allow each patient to process his or her reaction to the alcohol cues with a therapist before leaving the experiment. Thus, the therapist and study staff will know immediately if there is an adverse reaction to the cues. The therapist will address any adverse reactions to the cues at that time. In addition, therapists will now see all patients for an additional week of therapy. Thus, a plan is also in place for follow-up with these patients. During this session at week-33, the therapist will assess whether there were any adverse events, including a lapse that may have resulted from the cues. Any adverse events will be addressed in the session and reported to the PI. These procedures ensure that the patient does not leave the lab in a vulnerable state. If more than five individuals during the entire trial report having a lapse within 48 hours of the cue exposure session, we will discontinue the cue exposure assessment.

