#### **The impact of attrition.**

It is anticipated that some attrition will occur in this population, though we do not anticipate differential attrition by condition. A conservative estimate of 20% attrition over the course of data collection is assumed. Recently published evidence suggests an attrition rate of approximately 20% for other trials. In our own previous trials, we have seen attrition of around 20%. Thus, sample size will need to be increased by 20% over minimum requirements. After final attrition has been calculated, pretest differences on alcohol use and problems will be compared among individuals who finished the study versus those who did not and by condition, to determine whether these two groups differed in

systematic ways and whether these differences were related to treatment condition.

With respect to attrition during the follow-up period, all participants will update their address and phone number as well as the name and number of an individual who always knows how to reach them at every visit. The project coordinator will also contact each patient in between follow-up visits.

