### **Power for Specific Aim 1 - Detecting Treatment Effects on Alcohol Use Outcomes.**

The analyses of treatment effects will proceed via random coefficient regression utilizing a 2 (**Treatment**: 8 weeks of MBRP vs. 8 weeks of RP) x 5 (**Time**: Baseline, 4, 8, 20, 32 weeks) mixed general linear model. The primary outcome variable tested will be heavy drinking days (HDD), consistent with previous MBRP trials ([name] et al., 2014). Secondary analyses will explore related outcomes such as drinks per drinking day, scores on the ICS, and liver function tests, with appropriate control of Type I error. In each model, the key effect of interest will be the treatment X time interaction. Given the effect sizes in previous trials (small  $d=.23$  or  $f<.10$  to moderate  $d=.45$  or  $f=.20$ ), we conservatively estimate a small effect size (e.g.,  $f=.10$ ). A mixed model testing the between (treatment) X within (time) subjects interaction with a total of 180 participants (90 per treatment group) will give us well over .90 power, assuming alpha of .05 and a correlation of approximately .50 between repeated assessments. Given that we expect 20% attrition over the course of the trial, we will initially recruit ~226 participants.

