After the scan, a research assistant will escort the participants back to the changing room where their belongings are locked. Subjects in this group will be given their MBRP or RP condition assignment after the scan is complete in order to minimize any expectancy effects that may occur as a result of knowing their condition assignment before all pre-treatment measures have been taken. Subjects will be compensated \$30 for completion of the MRI scan I appointment.

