## **Goal-setting Session**

Subjects will have a 1-hour individual session with a trained therapist before starting the 8-week long program, resulting in a total of 9 individual therapy sessions. The purpose of this being a chance for the participant to discuss with their therapist their goals for the next 8 weeks in terms of drinking reduction goals or abstinence goals. Subjects will take a BAC test before the session starts.

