### **Check-in Session (33 weeks)**

Those subjects who participated in the MRI scan will return for a visit with a therapist one week after their second follow-up session. Before this session starts, participants will take a BAC test. During this session, the therapist will assess whether there were any adverse events, including lapses that may have resulted from the alcohol cues administered during the MR scan. Any adverse events will be addressed in the session and reported to the PI. At the end of their last session (33 weeks), participation in the study is complete.

Name of instrument/tool/procedure	Purpose (i.e. what data is being collected?)	Time to Complete
Questionnaire Measures Collected at Baseline Only		10 minutes
Demographics	

• A demographics questionnaire will be used to collect information on age, sex, marital status, SES, occupation, income, education, and race.

	
The Stages of Change Readiness and Treatment Eagerness Scale (SOCRATES)	

• SOCRATES (Miller & Tonigan, 1996) is an experimental instrument designed to assess readiness for change in alcohol abusers. The instrument yields three factorially-derived scale scores: Recognition (Re), Ambivalence (Am), and Taking Steps (Ts). It will be used to measure individual differences in motivation at baseline.

	

---

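### The trial-wide lapse count for the alcohol cue task has no scheduled check after the baseline scan, and the Scan I procedures omit the post-cue assessment that the risk section promises

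*Combined protocol and SAP*

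**What the plan says.** Section XVI, Exposure to Alcohol, says that "the cue exposure session takes place at baseline and at the second follow-up session (week-32"). It names craving and anxiety as possible reactions and then makes three commitments:

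- An assessment: "we will conduct an assessment with each participant after the cue exposure session to determine whether there is any residual craving or anxiety". Participants may also work through their reaction with a therapist before leaving.
- A therapist session at week 33 that asks about adverse events, including a lapse that may have resulted from the cues.
- Discontinuation of the cue assessment if more than five individuals in the whole trial report a lapse within 48 hours of the cue session.

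Section XV, Exposure to Alcohol, also names both scans as exposures. It adds that the risk matters particularly at the second, because many patients may by then be abstinent or drinking much less.

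Section XI sets out what staff do. For MRI Scan I: "After the scan, a research assistant will escort the participants back to the changing room where their belongings are locked". The participant then learns the treatment assignment and is paid. The next therapist contact is the goal-setting session: "Subjects will have a 1-hour individual session with a trained therapist before starting the 8-week long program". It covers drinking goals and a breath test. For Scan II, a therapist assesses residual craving and anxiety after the scan, and at week 33: "Those subjects who participated in the MRI scan will return for a visit with a therapist one week after their second follow-up session".

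**The concern.** The discontinuation rule is written as a count over the whole trial, and there are two alcohol exposures per scanned participant. Scheduled ascertainment follows only the second. Staff working from Section XI would omit, after the first exposure, an assessment that Section XVI appears to promise for each participant. They would also have no scheduled point at which to ask about a lapse in the following 48 hours.

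Two things are at stake. One is a participant-safety step that depends on which section staff follow. The other is the meaning of the count: a low number would look like evidence from both exposures when systematic questioning took place after only one. The DSMB reviews adverse events every three months (Section XVIII) and would read the count without knowing this.

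**Working it through.** **1. Commitments set against procedures**

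| Element | Section XVI | Scan I (Section XI) | Scan II (Section XI) |
|---|---|---|---|
| Cue exposure | Baseline and week 32 | Yes | Yes |
| Craving/anxiety assessment | After the cue session, not limited to one scan | Not listed in procedure or visit table | Listed, by a therapist |
| Therapist contact before leaving | Yes | Not listed | Implied by the therapist assessment |
| Lapse check | Week 33 is the only one named | None listed | Week 33 |
| 48-hour lapse count | Whole trial, individuals | No route stated | Via week 33 |

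The visit-table row for Scan I lists a breath test, a pregnancy test and the MRI. The goal-setting row adds return of the microbiome kit, but no lapse question. Even if the craving assessment is done after both scans, it takes place before the participant leaves and so cannot detect a lapse in the next 48 hours.

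**2. Could existing data fill the gap?** The Timeline Follow Back recalls 30 days and is next given at week 4. Whether it reaches the 48 hours after Scan I depends on the intervals from scan to goal-setting and from goal-setting to week 1. Neither is stated, and nothing links this instrument to the count.

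**3. Share of exposures at baseline**

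Inputs: "Given that we expect 20% attrition over the course of the trial, we will initially recruit ~226 participants"; "with a total of 180 participants (90 per treatment group"); "A conservative estimate of 20% attrition over the course of data collection is assumed".

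The plan's own figure first: 180 / (1 − 0.20) = 225, which agrees with the stated figure of about 226. (180 × 1.2 = 216 does not.)

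With N scanned at baseline and attrition d before week 32, the baseline share is N / (N + N(1 − d)) = 1 / (2 − d). N cancels, so the share does not need the unstated number scanned. It does assume that attrition among those scanned equals d.

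| d | 1 / (2 − d) |
|---|---|
| 0% | 50.0% |
| 10% | 52.6% |
| 20% (planned) | 55.6% |
| 30% | 58.8% |

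If all 226 were scanned, 226 × 0.8 ≈ 181 would have Scan II, and 226 / (226 + 181) = 55.5%.

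**4. Illustration of what ascertainment does to the rule**

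The documents give no lapse probability, so p per exposure is an assumption. Suppose all 226 are scanned, 181 return, p is equal at both scans, events are independent and no baseline lapse is reported spontaneously. The rule needs at least 6 individuals. With the second scan only, the chance is P(Bin(181, p) ≥ 6). With both scans, counting individuals, it is P(Bin(226, q) ≥ 6), where q = p + 0.8p(1 − p).

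| Assumed p | Week 32 only | Both scans |
|---|---|---|
| 1% | 1.0% | 22.1% |
| 2% | 15.7% | 81.9% |
| 3% | 46.0% | 98.2% |

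The assumptions of full scanning, equal p and no spontaneous reports make this an extreme contrast. It shows that the scope of the count matters to how the rule behaves. It is not a forecast.

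**The case against.** The strongest reply is that Section XVI names both cue sessions and then promises the assessment without limiting it to week 32. On that reading the craving assessment is planned after both scans, and Section XI merely fails to repeat it. This stands: for the assessment, the defect is a mismatch between sections, and the documents do not support saying that the plan contains no post-Scan I assessment. The reply does not reach the lapse check, which Section XVI itself ties to week 33.

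A second reply is that heavier follow-up after Scan II is a deliberate, risk-based choice, as Section XV explains. Scan I precedes treatment, entry requires a drink within the past 10 days, and abstinence is encouraged but not required. This has weight, and it shows that a lapse at baseline is undefined. But Section XV calls the risk particularly relevant at the second scan, not confined to it, and the rule is not limited to week 32.

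A reader might infer that baseline exposures contribute nothing to the count, or that it is zero for them by construction. The documents do not support that. The rule excludes no scan, breath tests precede every session, the Baseline Session text foresees participants reporting drinking, and Section XVIII sends adverse events to the principal investigator immediately. A lapse could surface by these routes; none is a scheduled question.

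A reader might also take 56% as the share of people unobserved, or as a maximum. It is neither: retained scanned participants do have one check at week 33, and the share rises with attrition. Nor can one state how many people would be scanned before the first week-33 visit. Only eligible and selected participants are scanned, they may opt out, and the remote version collects no MRI data.

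**Conclusion.** The concern holds as a contradiction within the protocol. The cue task is given twice and the discontinuation rule covers the whole trial, but the procedures schedule the post-cue assessment and the lapse check only for the second exposure. Baseline exposures have no scheduled route into the count.

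The exposures affected are half of the total with no attrition, about 56% at the planned 20% and about 59% at 30%, assuming that those scanned drop out at the same rate as the trial. The absolute number cannot be derived, because the number scanned is not stated. The consequence for the rule cannot be sized either without an assumed lapse probability, and it would be smaller to the extent that baseline lapses are reported spontaneously or are less likely than at week 32.

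This should be corrected: it bears on participant safety, and the correction is cheap.

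**What to change.** Reconcile Section XI (MRI Scan I, Goal-setting Session, Follow-up Assessment II and MRI Scan II, Check-in Session, and the visit table) with Section XVI (Exposure to Alcohol), so that they agree on three points: which scans the post-cue assessment follows, which scans the lapse count covers, and what a lapse means before treatment starts.

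- If baseline exposures are covered, the Scan I procedures should show how the assessment and any lapse are recorded, using contacts that already exist.
- If they are not covered, Section XVI should no longer describe the count as covering the whole trial, and reports to the DSMB should state that baseline exposures lie outside it.

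Which clinical rule applies is for the sponsor to decide. In either case the number scanned at each time point should be reported beside the count. The cost is protocol wording and possibly a few minutes at an existing visit.
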